14.2 Outcome measures

Table 6. Outcome measures

Outcome	Indicator
Primary Aim	
Incidence	Cumulative incidence of all cases (Pf infection) identified by passive surveillance in the locality subsequent to the first reported case during the study period (not including additional cases found through RACD). Cases include both locally acquired and imported infections.
Secondary aims (effectiveness)	
Exposure (seroprevalence)	Seroprevalence to markers of recent exposure using ELISA in end-line survey samples taken from residents in Target Areas near the end of the study (expected mid 2017), excluding index cases detected through passive surveillance.
Infection prevalence	Prevalence of infection by LAMP and QTNASBA testing for gametocytes in LAMP positives in end-line survey samples taken from residents in Target Areas near the end of the study (expected mid 2017), including index cases detected through passive surveillance.
Time to first local post-intervention incident case	Time to first incident local case in the Target Area subsequent to the intervention. Target Areas that receive a repeat intervention will qualify to be included again at subsequent interventions.
Proportion of imported incident cases	Proportion of imported incident cases in the locality subsequent to the first reported case will be measured through passive surveillance. Additional cases found through RACD will not be included.
Transmission potential (by genotyping)	Microsatellite genotyping will be performed on samples collected from index cases as well as secondary cases.
Secondary aims (feasibility)	
Coverage	Proportion of persons residing within approximately 200m (TPE localities) or 500m (RACD localities) of the index case who consented to participate in the study and who completed the initial procedures for their study arm (finger prick for RDT in the RACD arm, initial dose of DP in the TPE arm)
Adherence	Proportion of persons who completed 3 days of therapy among all individuals initiated on DP in the TPE arm, as assessed by pill count
Prevalence of SAEs related to treatment	Proportion of subjects experiencing SAEs deemed possibly, probably, or definitely related to DP or AL, out of the total number of subjects enrolled
Acceptability	Qualitative assessment (See Section 10)
Cost	Cost per index case-level intervention, cost per case averted.

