Based on equation 4 from Hayes and Bennett International Journal of Epidemiology 1999;28:319-32

Assumes that population is only those in the EAs that have at least one case.

Sample size calculation based on harmonic mean of population size.

Table 8. Detectable reductions in seroprevalence given varying assumptions about prevalence in the RACD arm

# Total localities with at least one index case	# localities per arm	Number assessed per locality (n)		Outcome proportion		Km (coeff of variation)	Z beta	Power
		RACD	TPE	RACD (π_0)	TPE (π_1)			
46.6	23.3	60	60	3.00%	1.35%	0.9	0.84	80%
62.3	31.2	60	60	2.40%	1.18%	0.9	0.84	80%
49.3	24.7	60	60	2.00%	0.83%	0.9	0.84	80%
50.8	25.4	60	60	1.50%	0.57%	0.9	0.84	80%

Based on equation 4 from Hayes and Bennett International Journal of Epidemiology 1999; 28:319-326

Assumes we are including only persons in the target areas in the denominator but evaluating at locality level

Assumes 3 per 100 is the background seroprevalence

Table 9. Sample sizes for primary and secondary aims.

Outcome	Result*	Actual sample size (Effective sample size, based on harmonic mean in clusters)
Primary aim		
Incidence	0.4% (RACD) vs. 0.2% (TPE)	55,928 (41,328)
Secondary aims (effectiveness)		
Exposure (seroprevalence)	2.4% (RACD) vs. 1.18% (TPE)	5400 not including index cases (3720)
Infection prevalence	n/a	5600 includes index cases
Time to first post-intervention incident case	n/a	55,928 (41,328)

Outcome	Result*	Actual sample size (Effective sample size, based on harmonic mean in clusters)
Proportion of imported incident cases	n/a	55,928 (41,328)
Transmission potential	n/a	Genotyping estimated to be performed in 800 index cases** and 35 infections from follow-up cross sectional survey
Secondary aims (feasibility)		
Coverage in TPE Arm	80% (95% CI: 77%-83%)	1782
Adherence in TPE Arm	80%	532
Prevalence of SAEs related to treatment	n/a	5400 not including index cases (3720)
Acceptability	n/a	5400 not including index cases (3720)
Cost	n/a	10 Target Areas/arm

*for some secondary outcomes, power calculations were not performed however effective sample size is shown.

** 200 index cases will be from the study area but an estimated 600 DBS that are already collected as standard surveillance from other parts of the country will also be used to characterize the background genotypes/transmission potential in Swaziland, as it relates to the transmission potential in the study areas.

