For the primary analysis comparing incidence between the TPE and RACD arms, we will follow an intention-to-treat (ITT) approach. We hypothesize that cumulative incidence in the TPE localities will be lower than in the RACD assigned localities. For the initial ITT analyses, estimates of effect will be unadjusted for any variables other than intervention group. To check for possible contamination of effects by proximity to an index case treated with TPE, a second set of ITT analyses will be conducted adjusting for intervention group and distance of index case from an index case assigned to TPE. Outcomes are assessed at the individual level. Because of the clustered nature of the data, our modeling approach will also adjust for correlation of observations by locality for analyses using the overall sample and by locality and index case for analyses using the Target Area sample. Generalized estimating equations (GEE) will be used to perform the proposed primary analyses. GEE accounts for the correlation of persons within clusters and localities. GEE estimates are consistent even if the correlation structure is miss-specified, though GEE's statistical efficiency improves as the working correlation structure more closely approximates the actual correlation structure. Thus, several working correlation structures suitable for the study's design will be considered (e.g., unstructured, Autoregressive order 1, exchangeable). The QIC statistic will be used to select the final working correlation structure. Robust Huber-White "sandwich" standard errors will be used to obtain correct inferences even if

the chosen correlation structure remains slightly miss-specified. Alpha will be set at 0.05 for all planned comparisons.

Should the preliminary analyses reveal an imbalance in the baseline covariates between the TPE and RACD arms, a second set of models will be run for all primary analyses. Adjusted models will reweight the data (through inverse probability weighting, or targeted minimum loss based estimation) to recover effect estimates that reflect an equal distribution of baseline covariates.

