Subgroup analyses: Although there is limited power with our constrained sample size, we will describe summary measures of incidence and intervention effects for some specific subgroups of interest within our study area population. Of particular interest are those who did or did not have insecticide spraying of their household areas, strata of risk as determined by the National Malaria Control Program, and season of index case presentation.

Secondary analyses:

Assessments of secondary outcomes will also be conducted using GEE techniques to account for the clustered nature of the data collection as described above. Secondary analyses for prevalence and seroprevalence are restricted to individuals in the Target Areas who will be participating in blood testing surveys conducted towards the end of the study (expected mid 2017). As noted, for analyses of outcomes in the Target Area sample, clustering by both locality and index case area will be accounted for in the modeling approach. To account for possible contamination by proximity to another index assigned to the TPE arm, models will also include adjustment for distance to the nearest index case treated with TPE. Planned secondary analyses and hypotheses are as follows:

Hypotheses regarding the effectiveness of TPE compared to RACD:

1. Comparison of seroprevalence using antibodies to markers of recent exposure. Using the samples collected in the end-line survey near the end of the study (expected mid 2017), we expect that seroprevalence will be lower in the Target Areas receiving TPE than in those receiving RACD.
2. Comparison of prevalence of malaria infection. Using the samples collected in the end-line survey near the end of the study (expected mid 2017), we expect prevalence to be lower in the Target Areas receiving TPE than in those receiving RACD.
3. Comparison of proportion of incident cases that are imported. We expect that local transmission will be reduced by TPE and thus the proportion of subsequent cases imported will be higher in the TPE arm than in the RACD arm. This outcome will be summarized at the locality level and analyzed with locality as the unit of analysis.

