4. Comparison of time to first post-intervention incident infection. We hypothesize that time to the first post-intervention index case within the Target Area will be longer for Target Areas receiving TPE compared to those receiving RACD. Analysis for this outcome will use a standard cox proportional hazards model to estimate the time to a subsequent incident infection among individuals in the Target Area.
5. Comparison of transmission potential using genotyping. Microsatellite genotyping will be used to measure transmission potential. DNA samples for genotyping will be collected from index cases and secondary cases. Based on malaria rates in Swaziland over the past three years, we expect approximately 200 index cases over the study period and 35 infections from the follow-up cross sectional survey (1.6% prevalence in the TPE arm and 0.4% in the RACD arm). We expect transmission potential to be lower in the TPE versus RACD arm. Relatedness of infections within Target Areas and within localities will be used as a surrogate for transmission potential.

Planned Analyses of Operational Feasibility and expected findings:

1. Coverage of the intervention. The numbers and proportion of the population completing finger prick testing (if RACD arm) or receiving at least the first dose of medication (if TPE) will be calculated by arm. The proportion of the individuals living in Target Areas around an index case that receive the TPE intervention is expected to be 80% with a 95% confidence interval from 76% to 84%.
2. Adherence to TPE. In the subsample of Target Areas surrounding the first index case in each locality assigned to TPE, we will assess adherence to the 3 day regimen of DP in TPE using pill count. We expect adherence to be 80%.
3. Safety of the TPE treatment. The number and percent of individuals experiencing an adverse event will be recorded by study arm. We expect that compared to RACD, TPE will be safely administered with few or no serious adverse events related to treatment, and no difference in SAEs compared to AL based on analysis of the adverse events report forms.
4. Acceptability of the intervention. See Section 10.
5. Costs per incident infection and per population. Detailed costing will be performed in 10 Target Areas per arm. We expect that costs per incident infection and per population for implementing the TPE intervention will be no higher than for RACD, the current standard of care.

15 Advisory Committee

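### Time to first local case: the Cox model as worded conflicts with the plan's own clustering rule, unit and event, and over-rejects if followed literally unless events are very few

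*Combined protocol and SAP*

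**What the plan says.** **Time to first local case.**

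- Section 14.2, Table 6, defines the outcome as "Time to first incident local case in the Target Area subsequent to the intervention", and adds: "Target Areas that receive a repeat intervention will qualify to be included again at subsequent interventions".
- Section 14.4, secondary item 4, hypothesises that "time to the first post-intervention index case within the Target Area will be longer" under TPE. It then changes unit and event: "Analysis for this outcome will use a standard cox proportional hazards model to estimate the time to a subsequent incident infection among individuals".
- Section 14.3, Table 9, has a row "Time to first post-intervention incident case" with 55,928 people (41,328 effective), which is the locality at-risk population. Section 9.4 collects the data by locality.
- The paragraph introducing the secondary analyses in section 14.4 says that secondary outcomes use GEE and that, for Target Area outcomes, "clustering by both locality and index case area will be accounted for in the modeling approach". The primary analysis paragraph says much the same.

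**Primary outcome.** Section 14.4 uses GEE, with the working correlation chosen by QIC. Huber-White "standard errors will be used to obtain correct inferences even if" that structure is somewhat wrong. No small-sample correction, t reference or randomisation-based test is mentioned. On covariates: "For the initial ITT analyses, estimates of effect will be unadjusted for any variables other than intervention group".

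**The concern.** Randomisation is by locality. Target Areas in one locality share transmission conditions, and a repeat Target Area contributes more than one record. A Cox model without a cluster term treats all records as independent, so chance differences between localities could be read as TPE delaying local cases.

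The unit and event matter too. In Table 2, 97 of 333 cases (29%) were imported, so moving from local cases to any index case adds 97/236 = 41% more events. Sections 4.4 and 7.2 make secondary cases found by RACD into index cases, while Table 3 bars screen-detected infections from being index cases. Table 6 excludes RACD-found cases for incidence and for proportion imported, but its time-to-case row is silent. Read one way, the event could be found by screening mainly in the control arm.

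For the primary GEE, the uncorrected sandwich can be too small when there are few, unequal clusters.

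**Working it through.** The plan gives no power or error figure for the time-to-case outcome, so there is none to reproduce. Re-entering Table 2 does reproduce its totals (236 local, 97 imported, 333 cases; 55,928 at risk) and the harmonic mean of 656 over 63 case localities. Their sizes run from 224 to 3,043, CV 0.65.

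**1. Event rate (anchor plus assumption).** Local cases per person-month: 236 / 55,928 / 31 months = 0.000136. Times 30 people (section 14.1) = 0.0041 per Target Area-month; times 53 (section 4.4) = 0.0072. An assumed relative risk near an index case of 1 to 5 gives 0.004 to 0.036. The 4.6 in section 1.3 is an odds ratio for LAMP infection, so it does not fix this multiplier.

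**2. Set-up.** There are 205 Target Areas: Table 2 cases scaled to the 200 of section 14.1, at least one per locality, the largest 41/333 x 200 = 25. Follow-up is uniform over 1-21 months (assumed; mean 11). Check: 205 x 11 x 0.0041 = 9 events. Locality frailty is gamma with CV 0.5-0.9 (assumed); Table 2's local counts suggest 0.65-0.82 and section 14.3 assumes 0.9 for its power calculation. There were 4,000 runs per setting.

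**3. Null rejection of the unclustered Cox test, nominal 5%, Target Area as unit.**

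| Events (about) | CV 0.5-0.9 | CV 0.75 |
|---|---|---|
| 9 | 2-2.5% | |
| 20 | 5.4-9.5% | 7-8% |
| 37 | 7.6-14.9% | 11-12% |
| 58 | 10.3-19.8% | 15-17% |

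Two repeat simulations at CV 0.75 gave 8.5-8.6%, 12-12.4% and 14.5-15.5% for the last three rows. With no frailty the test rejected 4.0-4.7%, so the excess comes from clustering.

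**4. Individuals as unit** (205 x 30 = 6,150 people; 900 runs, Monte Carlo error about 1-1.5 points). With 0.15%, 0.36%, 0.73% and 1.3% having events (about 9, 22, 45 and 80 people), rejection is 2-4%, 6-11%, 8-20% and 15-28%. The number of events matters more than the unit.

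**5. Remedies, Target Area as unit, 20 or more events.** Locality-robust z-test 6.6-8.9%; leave-one-locality-out jackknife with t 3.4-5.0%; permutation within strata 4.3-5.5%.

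**6. Unequal catchments.** Target Areas are 200 m in TPE (extended if fewer than 30 people are enrolled) and 500 m in RACD. By area the ratio is (500/200)^2 = 6.25; the 500 m population is not given. With no drug effect, CV 0.75 and hazards 0.01-0.02 (400 runs each), the within-strata permutation test rejects 4-6% with equal catchments. It rejects 15%, 27-36% and 61-72% if the RACD area carries 1.5, 2 or 3 times the hazard (assumed ratios). The figures in step 5 therefore hold only for equal catchments.

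**7. Primary GEE, no effect.** At 0.4% and k = 0.9, over four assumed block designs, the plain sandwich z-test with exchangeable correlation rejects 5.5-6.2%; Mancl-DeRouen with t gives 4.5-4.9%. Re-randomising Table 2's own counts, less each locality's first case:

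| Method | Three designs | Matched pairs |
|---|---|---|
| Plain sandwich | 7.1-8.8% | 5.0% |
| Mancl-DeRouen with t | 6.0-7.2% | 3.7% |
| Permutation in blocks | 5.0-5.2% | 5.0-5.2% |

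**The case against.** A reader might infer from item 4 that the plan ignores clustering for this outcome. The documents do not support that: section 14.4 commits to it twice, once in the paragraph that introduces item 4. What stands is a conflict. The tool named there is GEE, item 4 names a different model and calls it standard, and no text joins the two or deals with repeat entry.

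The event is also largely settled. The study summary, section 3 and Table 6 all say local; only item 4 and a Table 9 label are looser. Table 9 is a listing, and its footnote says power was not calculated for some secondary outcomes. This narrows the point without removing the mismatch over individuals and Target Areas.

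The Cox magnitudes rest on assumed hazards, frailty and follow-up, and at about 9 events the error runs in the safe direction. That is correct.

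For the primary analysis, the missing correction is inferred from silence, and selection by QIC was not simulated. A reader might also infer that covariates enter only after a positive balance check, and that this inflates error. The plan does not work that way. It adjusts for distance to a TPE-assigned index case in a second set of analyses whatever the balance, and handles imbalance by inverse probability weighting or targeted minimum loss estimation. In simulation, weighting rejected 5.6-6.2% against 5.6% unadjusted; the targeted method was not tested.

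**Conclusion.** The point holds for one secondary outcome. Item 4 conflicts with the clustering rule in section 14.4, with Table 6 and with Table 9. Followed literally with Target Areas as the unit, its 5% test rejects about 5-10% with some 20 events and 10-20% with some 58, given locality frailty CV 0.5-0.9. A plain locality-robust z-test would still reject about 6-9%. The unequal radii are a separate source of bias that no variance correction removes; its size is unknown because the 500 m population is not given.

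The primary GEE part is minor: about 6% at k = 0.9, and 7-9% on Table 2's counts under some block designs. It does not support a claim that the primary result would be seriously unreliable. Block sizes and population cut-points are not in the supplied text, so the four designs are assumptions.

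**What to change.** **Time to first local case**

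1. In Table 6, item 4 and Table 9, state one unit (the Target Area) and one event (the first passively detected local case, excluding cases found by RACD screening).
2. Count events within the same fixed radius of the index case in both arms, for example 200 m. Case investigation already records home coordinates.
3. Replace the standard Cox model with one that has a locality frailty or locality-clustered variance and covers repeat entries.
4. Take the p-value from permuting localities within the actual randomisation blocks. Take the interval from inverting that test, or from a locality jackknife with t.

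The cost is SAP wording and modest code, no new data, and fewer RACD events counted. Apparent power falls. At hazard ratio 0.5, CV 0.75 and equal catchments, with hazards 0.01, 0.02 and 0.036, permutation gives 20%, 27% and 36%. The naive test gives 23%, 40% and 56%, but rejects 7%, 12% and 16% under the null.

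**Primary GEE (minor)**

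Use permutation within the actual blocks, or Mancl-DeRouen with t as a partial correction. In simulation at 0.4% against 0.2% and k = 0.9, power goes from 67.7% uncorrected to 64.7% or 63.9%, a cost of 3-4 points. Part of the uncorrected lead is its inflated error. These figures compare the tests with one another and are not a re-estimate of Table 7.

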1. To determine the feasibility of obtaining at least 80% coverage of TPE, and compare coverage to that attained using RACD. Coverage will be defined as receipt of and adherence to the first dose of DP within initial visits by the study team in the TPE arm or receipt of a blood test in the RACD arm. Our **hypothesis** is that the coverage attainable for TPE will be at least 80%. We also hypothesize that coverage for TPE will be equivalent to RACD but we will not be powered to prove this hypothesis.
2. To measure adherence to a 3-day regimen of DP administered by modified DOT delivery system in the TPE arm. We hypothesize adherence will be 80%.
3. To compare potential serious adverse events associated with TPE and RACD. We will test the hypothesis that the risk of serious adverse events will not be higher in individuals receiving TPE versus RACD.
4. To compare the acceptability of TPE versus RACD as assessed by refusal rates and a qualitative assessment. We hypothesize that TPE will not be inferior to RACD in terms of acceptability and may be more desired.
5. To compare the costs of TPE versus RACD. We will test the hypothesis that the costs per event will not be higher for individuals receiving TPE compared to RACD and may be cost-saving.

4 Study design & methods

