8.1 Overview

The safety risks associated with participation in this trial are expected to be minimal. AL, the current standard of care in Swaziland, is generally well tolerated and, at least by passive monitoring, has been associated with only minimal adverse effects in Swaziland. DP is one of the ACT regimens recommended by the WHO[23], and is recommended as a second line treatment for uncomplicated malaria in many countries[24]. The safety and tolerability of DP have been closely evaluated in clinical trials evaluating DP for treatment and prevention of malaria, and DP has been shown to have an excellent safety profile[10, 11, 25, 26]. In the TPE arm, prior to drug administration, subjects will be asked about known allergy, past adverse reactions felt to be associated with treatment, and other contraindications (see Table 3) and will be excluded from taking drug if such a history is reported.

Adverse event monitoring of SAEs potentially related to AL or DP will occur passively. Subjects will be instructed to seek care at their local health facility if they experience any serious adverse reactions that may be related to AL or DP. Health facility physicians will determine if a participant should continue or stop treatment due to safety concerns. Health facility staff will be asked to notify study staff of all adverse events. For any adverse events that are reported in either arm, we will attempt to assess causality by collecting additional data on the relationship between the drug and the event. This information will be reported and reviewed by the Pharmacovigilance and Adverse Drug Reactions Committee (the Data Safety & Monitoring Board for this study).

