8.4 SAE report forms

For each serious illness identified, an adverse event report form will be completed (Appendix S). The following information will be recorded for all experiences that are reported:

- Description of the subject (ID number, age, gender, weight)
- Name of the event
- Description of the event and management of illness
- SAE criteria met
- Date of event onset, date of resolution, and date event reported
- Maximum severity (Appendix T)
- Causality and expectedness
- Drug history (names, doses, dates administered for all drugs taken one month prior)
- Past medical history, including known allergies
- Management and outcome of the event

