DD/MM/YY	automatically generated per 22a	 yes  no	half tabs  1  2  3 full tabs (120/20 or 320/40)  0  1  2  3  4  5  6  7  8  9	half tabs  1  2  3 full tabs (120/20 or 320/40)  0  1  2  3  4  5  6  7  8  9	

For return visits for pill count, allow editing of above table for all individuals.

26. Ask: Have you experienced any potential side effects from the medication?

Yes No

26a If YES, specify:

- cough
- fever
- headache
- lack of energy
- abdominal pain
- pale complexion or pallor
- yellow discoloration of skin or eyes (jaundice)
- weakness
- joint pain
- dark urine
- nausea
- vomiting
- diarrhea
- chest pain
- heart palpitations
- other (specify _____)

If YES, complete Appendix S. **Adverse drug reaction (ADR) Report Form**

27. Please explain all measures taken to alleviate these adverse reactions related to the drug

28. Other comments _____

Thank you for our participation in this study.

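### The by-arm safety analysis in 14.4 counts any adverse event, Table 6 counts treatment-related SAEs, and only the TPE questionnaire turns a solicited side effect into a report form

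*Combined protocol and SAP*

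**What the plan says.** **Definition of the event.** Table 6 (14.2) gives the safety outcome as: "Proportion of subjects experiencing SAEs deemed possibly, probably, or definitely related to DP or AL, out of the total number of subjects enrolled". Feasibility aim 3 in Section 3 is also about serious events: "We will test the hypothesis that the risk of serious adverse events will not be higher in individuals receiving TPE versus RACD". The safety item in 14.4 opens with an unqualified adverse event, counted by arm: "The number and percent of individuals experiencing an adverse event will be recorded by study arm". It sets no condition on seriousness or relatedness and no denominator. Its second sentence returns to SAEs and expects "no difference in SAEs compared to AL based on analysis of the adverse events report forms".

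**How events are found.** Section 8.1: "Adverse event monitoring of SAEs potentially related to AL or DP will occur passively". Section 8.4: "For each serious illness identified, an adverse event report form will be completed", the form being Appendix S.

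**What the questionnaires do.** Appendix K (TPE individual form) item 26 comes directly after the pill-count table and asks: "Have you experienced any potential side effects from the medication". It lists 15 named symptoms, including cough, headache and nausea, plus an open category. Any yes sends staff to Appendix S. Appendix I (RACD individual form) ends with the RDT and DBS items and has neither a side-effect question nor a link to Appendix S.

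**The concern.** An analyst who works from 14.4 would tabulate everyone with any recorded adverse event, by arm. The only adverse-event source that 14.4 names is the report forms. In TPE those forms can come from a checklist put to participants at any severity. In RACD they come from passive reporting. The two percentages would then measure different things, and TPE could look less safe partly because its participants were asked. The denominator is also unclear: item 26 appears to reach only the pill-count subsample, whereas Table 6 divides by everyone enrolled.

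Safety against RACD is a stated secondary aim and would inform any decision to adopt TPE, so the table should have one meaning.

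**Working it through.** **1. The plan's own numbers.**
- Target Area sample (14.1): 200 index cases × 30 people × (1 − 0.10 repeats) = 5,400. This matches Table 9, which lists 5,400 for the SAE outcome and gives no expected rate or power.
- TPE people treated (14.3): 66 × 30 × 0.9 = 1,782, as stated.
- RACD remainder: 5,400 − 1,782 = 3,618.

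**2. Drug exposure by arm.** Section 1.3 reports 42 RDT positives among 8,355 screened (0.5%). In RACD, 3,618 × 42/8,355 ≈ 18 people would be referred for AL, against about 1,782 given DP.

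**3. Event count under Table 6.** Section 17.3 cites 4 DP-related SAEs among 1,468 treated children. At that rate, TPE gives 1,782 × 4/1,468 ≈ 4.9. Using the same rate for AL (an assumption), RACD gives 18.2 × 4/1,468 ≈ 0.05.

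**4. Forms generated by item 26.** The adherence subsample is 22 localities × 30 = 660 (14.1), or 660 × 0.80 = 528 if 80% receive DP. The yes-rate is an assumption. The 3.3% used here is the vomiting figure in 17.3, from children under five with clinical malaria, so it only illustrates.
- 528 × 0.033 = 17.4 and 660 × 0.033 = 21.8, or 17 to 22 forms.
- If item 26 were put to all 1,782: 1,782 × 0.033 = 58.8.
- RACD by the same route: none.

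**5. Ascertainment alone.** Suppose 3.3% of people in both arms have a listed symptom whatever the intervention, 660 TPE people are asked, and passive reporting captures 10% of the rest (assumptions).
- TPE recorded: (660 × 0.033 + 1,122 × 0.033 × 0.10)/1,782 = (21.78 + 3.70)/1,782 = 1.43%.
- RACD recorded: 0.033 × 0.10 = 0.33%.
- With no passive capture: 21.78/1,782 = 1.22% against 0%.

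The arms differ here with no true difference between them.

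**6. Triggers side by side.**

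| Source | Who is asked | Leads to Appendix S? |
|---|---|---|
| 8.4 | Passive, both arms | Serious illness only |
| Appendix K item 26 | TPE | Any yes |
| Appendix I | RACD; no question | No |
| Appendix C item 31 | Index cases, both arms; RACD secondary cases (7.2) | No |
| Appendix P item 9 | Both arms at end-line, if study malaria drug taken | No |

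**The case against.** The case for the plan has several sound parts.

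- **The report-forms clause belongs to SAEs.** In 14.4 it sits in the second sentence. The summary, the aim and Table 6 all speak of serious events, so the adverse-event sentence may be loose wording. This stands. The mixing of event types occurs only if that sentence is taken literally, but nothing in the documents tells the analyst not to.
- **Seriousness can be filtered.** Section 8.4 lists the SAE criteria met, and Appendix S records hospitalisation, death, disability, severity and relatedness. This also stands, so no new seriousness field is needed. What cannot be recovered is whether an event was solicited or reported passively.
- **RACD is not wholly unquestioned.** Secondary cases, the residents referred for AL, receive the case investigation with its side-effect item, and 8.1 asks health facilities to report all adverse events. This is correct, but those questions do not lead to Appendix S.
- **The arms differ in exposure.** Most RACD participants take no drug, so a TPE excess is not all artefact. This stands.

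A reader might infer that solicited mild symptoms could set off the stopping guideline. Section 16.3 does not support that: it uses serious events judged causally related to study drug. Only related SAEs first learned of at the pill count could be found unequally there, and the documents give no figure for how many.

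**Conclusion.** The point holds as an inconsistency in definition and data capture. Section 14.4 and Table 6 name different safety outcomes, and 8.4 and Appendix K give different triggers for the same form, one of which operates in TPE only. If the 14.4 sentence is followed, about 17 to 22 TPE forms (at an assumed 3.3% yes-rate, with item 26 asked at the pill count) would enter a by-arm percentage with no RACD counterpart. That item 26 is confined to the pill-count visit is inferred from its position on the form.

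Two stronger readings are not supported. A reader might infer that the planned SAE comparison itself counts mild events against TPE; under Table 6 or the aim they would be filtered out. A reader might also compare the item 26 forms with the roughly 5 expected related SAEs and treat the ratio as a measure of bias. The two counts rest on different bases (a subsample and 1,782 people), and part of any excess is real exposure to DP. Safety is a secondary outcome with no power calculation and the correction is small, but it should be made before data are tabulated by arm.

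**What to change.** 1. In 14.4 item 3, replace the unqualified adverse event with the Table 6 outcome: SAEs that meet 8.2 and are judged possibly, probably or definitely related, over all enrolled. Citing 8.2 alone would not be enough, because it carries no relatedness condition.
2. Report item 26 side effects as a TPE-only description, with the people asked item 26 as the denominator.
3. Reconcile the Appendix S triggers in 8.4 and Appendix K.
4. Add one field to Appendix S recording whether the event was solicited or passively reported.
5. Show the between-arm comparison for all related SAEs and, in a separate row, for those found by the passive route common to both arms. No known related SAE is then dropped.

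The cost is a wording change in the analysis plan, one extra table row and one form field.
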